4.2.2 Control group

- Control group will not be asked to download any digital applications but only receive the usual care by the hospitals.

4.3 Patients' inclusion and exclusion criteria are as follow:

4.3.1 Inclusion criteria:

- Age: 18 years and above
- Diagnosed with selected non-communicable diseases (NCDs): hypertension, diabetes mellitus, heart failure or asthma for at least 6 months
- Prescription generated from one of the following specialty clinics: Medical, Cardiology, Diabetes Mellitus or Asthma clinics
- Medications are prescribed in previous 3 months and refill at the point of recruitment
- Morisky Medication Adherence Scale (MMAS) score < 6
- More than three medications daily or two medications with multiple dosing intervals.
- One or more hospital admissions in the prior 24 months
- Understand and able to command in English and own a smartphone

4.3.2 Exclusion criteria:

- Medications prescribed from other institution providers
- Existing mobile health app or medication reminder app user
- Pregnant
- Cognitively impaired
- Prisoners
- Bed-bound
- Severe diseases/comorbidities – terminal cancer, psychiatry, etc

4.3.3 Withdrawal criteria:

Participants can choose to withdraw at any time for any reason, specified or unspecified, and without prejudice to their care. Participants may be withdrawn if the investigator feels that it is not for the participants' best interest to continue. The following is a list of possible reasons for study intervention discontinuation:

- Screening failure

- Participant withdrawal of consent
- Participant is not compliant with study procedures
- Protocol violation requiring discontinuation
- Lost to follow-up
- Request from sponsor for early termination of study
- Participant death

Withdrawn participants will not be replaced. It will be documented whether or not each subject completes the clinical study. If the Investigator becomes aware of any serious, related adverse events after the subject completes or withdraws from the study, they will be recorded in the source documents and on the Case Report Form (CRF). The Investigator will contact participants who are lost to follow-up. Contacts attempts with such subjects will be documented in the participant's records (e.g., times and dates of attempted phone contact, receipt for mailing a registered letter, etc.).

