Indirect medical or patient out-of-pocket cost such as transportation costs, productivity losses, caregiver costs and waiting time in outpatient visit will be collected with the used of cost questionnaires to the participants. Patients will be requested to report the resource utilization over the past 3 months during the first time after recruitment(baseline) and after every 3 months (at 3 and 6 months). Transportation costs included parking fees. Patient time costs will be calculated based on waiting time in outpatient visit with the wages per hour of patient. Rate of wages per hour will be estimated based on patient's reported income per hour. Productivity losses will not be accounted for patients who are retired and jobless. This economic cost will help to evaluate the economic impact of CareAide from patients' perspective. All costs will be valued in Malaysia Ringgit (MYR).

v. Health-related quality of life (HRQoL) of patients

The overall health state and quality of life will be collected with the EuroQol-5D (EQ-5D-5L) and Short Form 36 Health Survey (SF-36) questionnaires to determine quality-adjusted life years (QALYS) over 3- and 6- months follow-up time. This study will use the EQ-5D-5L and SF-36 surveys to assess the HRQoL of chronic disease patients. The EQ-5D-5L instrument of the EuroQol is a validated tool to measure the health status of various groups in various diseases. This tool composed of five dimensions: mobility, self-care, usual activities, pain/discomfort and anxiety/ depression (Lins et. al., 2016). Another questionnaire SF-36 is a self-reported measure of health with 36 items which cover eight domains of health. The eight domains including vitality, mental health, physical functioning, bodily pain, general health perceptions, physical role functioning, emotional role functioning and social role functioning (Lins et al., 2016). Both tools consist of questionnaires whereas EQ-5D-5L consists of additional visual analogue scale. These tools will be conducted via face-to face or phone interview to assess the health status of respondents.

Trained research personnel will explain the purpose of the study and obtain consent of the participants before distributing or administering the questionnaires. Participants will then be distributed with questionnaires. EQ-5D-5L and SF-36 have different languages versions of the validated phone interview or face-to face questionnaires included English, Malay, Tamil and

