
$n_i =$ sample size required for each group ($i = 1,2$)

$Z_{\alpha/2} =$ Assumed type I error: α equal to 5%, then $Z_{0.05/2} = Z_{0.025} = 1.96$ (From Z table)

$Z_{\beta} =$ Assumed power of 80% $Z_{\beta} = 0.84$

$W =$ Willingness to pay threshold

$p =$ Expected correlation between difference in costs (ΔC) and effects (ΔQ)

$\Delta Q =$ Expected difference in mean effects

$\Delta C =$ Expected difference in mean costs

$Sd_Q =$ Expected standard deviation for the effects

$Sd_C =$ Expected standard deviation for the costs

To our knowledge, there is no published study has evaluated the direct and indirect costs and quality of life associated with mobile health app for the management of non-communicable diseases. Therefore, the calculation is based on the assumption and few literature results. According to a study published in Malaysia, RM 2499.15 is required for the managing of patient complicated with diabetes and heart failure after the first event (Shafie & Ng, 2020). The cost from the study is adjusted according to Consumer Price Index 2022. The cost difference between treatment group is considered as around 30% as reported by the use of mobile app in the management of heart failure study (Cano Martín et al., 2014). A minimum difference of 0.01 is estimated in term of QALY in favour of mobile health app user. Sd_c and Sd_Q are assumed as RM1000 and 0.01 respectively. The willingness to pay threshold is set at RM 28,470 per QALY as reported by Lim et al. (2017). The correlation coefficient is set at minimum 0.1 as estimated from cost-effectiveness analysis of a mobile-based intervention for patients with type 2 diabetes mellitus conducted by Li et al. (2021). A number of 150 patients (75 per study group) is required to detect at least 80% power assuming a two-tailed test and alpha of 5% between treatment group. The sample size will be rounded up to 200 patients to account for a possibility of 20% attrition. The sample size obtained is corresponding to the sample size applied in Li et al. (2021) cost-effectiveness analysis study.

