An economic evaluation will be conducted from a payer and societal perspective. Costs and outcomes will be discounted at 3% per year (Shafie et al., 2019) as the results will be extrapolated to examine costs and outcome over a year.. Cost effectiveness analysis will be estimated based on the results of cost data and EQ-5D-5L to calculate the incremental cost per quality adjusted life year (QALY) gained. Total incremental cost effectiveness ratio (ICER) will be calculated by dividing the difference between the cost of CareAide intervention group and control group by the difference between the QALYs of CareAide intervention group and control group. Sensitivity analysis will be performed by bootstrapping technique to ensure or examine the robustness of ICER. Then, cost effectiveness acceptability curve (CEAC) will be created to estimate the proportion of the result being cost-effective in relation to the Willingness-to-Pay (WTP) threshold.

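### The ICER is planned from the raw between-arm cost difference although pre-baseline resource use is collected, which forgoes precision on the endpoint that sized the trial

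*Combined protocol and SAP*

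**What the plan says.** - **Collection.** Section 4.4.1.2, under item iv (Indirect Medical Cost), asks this of patients: "report the resource utilization over the past 3 months during the first time after recruitment(baseline) and after every 3 months (at 3 and 6 months". That item covers transport, lost productivity, caregiver cost and waiting time. Item iii (Direct Medical Cost) covers visits, medicines, admissions and tests, and gives no window before baseline.
- **Analysis.** Section 4.6 obtains the ICER by "dividing the difference between the cost of CareAide intervention group and control group by the difference between the QALYs", examines it by bootstrap and draws a cost-effectiveness acceptability curve (CEAC), from payer and societal perspectives. No covariate is named. The only linear regression in that section concerns predictors of quality of life.
- **Sizing.** Section 4.5 first derives 970 patients from adherence, judges that too large, and recalculates from the cost-effectiveness endpoint, two-sided at 5%: "A number of 150 patients (75 per study group) is required to detect at least 80% power". This is then rounded up to 200 for 20% attrition.

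**The concern.** A cost measure is taken before treatment starts and then plays no part in estimating incremental cost. On the plan's own inputs, cost supplies nearly all the variance of the endpoint that fixed the sample size, so a covariate that predicts cost would help most there.

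There is reason to expect some prediction. Four diseases are pooled across three hospitals, and Section 4.3.1 requires "One or more hospital admissions in the prior 24 months". Some patients will therefore enter soon after an admission and others long after one, so recent cost should differ widely between patients. If part of that carries into follow-up, the unadjusted ICER and CEAC will be less precise than the same patients could support.

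The point concerns the cost numerator only, not MMAS-8, PDC or utility.

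**Working it through.** **Inputs from Section 4.5.** Willingness to pay W = 28,470; SD of cost 1000; SD of QALY 0.01; cost-QALY correlation 0.1; QALY difference 0.01. For cost, "RM 2499.15 is required for the managing of patient complicated with diabetes and heart failure after the first event", and "The cost difference between treatment group is considered as around 30"%, so ΔC = 0.30 × 2499.15 = RM749.75. The direction of ΔC is not stated. A price-index adjustment is mentioned, but only the one figure is printed.

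**1. Reproduce the plan's figure.**
- Net-benefit variance V = 1000² + (28,470 × 0.01)² − 2 × 28,470 × 0.1 × 1000 × 0.01 = 1,000,000 + 81,054 − 56,940 = 1,024,114.
- With the app arm costlier, the net-benefit difference is 284.70 − 749.75 = −RM465.05.
- n = 2 × (1.96 + 0.84)² × 1,024,114 / 465.05² = 74.25, so 75 per group. This matches.
- With the 30% as a saving, the difference is 284.70 + 749.75 = RM1034.45 and n = 15.0, or 15-16 per group. This does not match.

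**2. Unadjusted position.** 100 enrolled per arm less 20% leaves 80. SE = √(2 × 1,024,114 / 80) = RM160.0, so the half-width is 1.96 × 160.0 = RM314. Power = Φ(465.05/SE − 1.96) = 82.8%. At 75 per arm it is 80.3%.

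**3. Adjusted position.** The correlation r of baseline with follow-up cost is an assumption; the documents give none. Adjustment multiplies the cost variance by (1 − r²). The cost-QALY term can be handled in two ways:
- covariance held fixed: V = 1,000,000(1 − r²) + 24,114;
- correlation held at 0.1: V = 1,000,000(1 − r²) + 81,054 − 56,940√(1 − r²).

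At r = 0.5 these give 774,114 and 781,743. At 80 per arm:

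| Assumed r | Half-width (RM) | Power if app arm costlier | Gain (points) |
|---|---|---|---|
| none | 314 | 82.8% | – |
| 0.2 | about 307 | 84.2% | about 1.4 |
| 0.3 | about 300 | about 86% | about 3 |
| 0.5 | about 273 | 91.4-91.7% | about 9 |
| 0.7 | 226-230 | about 98% | about 15 |

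The half-widths do not depend on the sign of ΔC. If ΔC is a saving, unadjusted power is already about 100% and the last two columns do not apply.

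**4. Sensitivity to the printed cost.** If a price uplift of, say, 5% (an assumption) were applied on top of RM2499.15, the gain at r = 0.5 and 80 per arm would be about 7 points.

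**The case against.** The strongest reply is that nothing is broken. The unadjusted difference is a legitimate estimator, the RM1000 is already an unadjusted SD, and the 80% target is reached without any covariate. That stands, and it limits the point to efficiency. Three stronger readings are tempting and are not supported.

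- **Power is lost.** A reader might infer that the planned analysis falls short of its target. It does not: 80.3% at 75 per arm and 82.8% at 80. The difference is an optional gain forgone, and its size depends on r. Recalled 3-month cost is noisy, so the lower rows of r may be the realistic ones.
- **Chance imbalance biases the ICER.** Randomisation leaves the raw difference unbiased on average. Imbalance in prior cost is already part of the sampling error that the bootstrap expresses, so it is the same precision issue and not a second harm.
- **Baseline admission cost is collected and ignored.** The 3-month report is stated only under indirect cost. For admissions and other direct costs, the plan does not say that a pre-baseline figure is obtained, and patient-borne cost alone is not the matching covariate for the payer analysis.

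It is also fair to say that Section 4.6 specifies no net-benefit test, so the power figures describe the sizing formula. Interval width is the more relevant measure for a bootstrap and CEAC. Finally, the plan is silent on adjustment and does not forbid it. That favours settling it in advance, since adding a covariate after seeing the data in an open-label trial would invite criticism.

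**Conclusion.** The point holds as a precision improvement, not as an error in the estimate. Adjusting for baseline cost would narrow the net-benefit interval by about 2% at r = 0.2 (314 to 307) and about 13% at r = 0.5 (314 to 273), whichever arm costs more. The power gain of roughly 1.4 to 15 points rests on two things the documents do not settle: the value of r, and a 30% cost difference that runs against the app, which is the only direction that reproduces 75 per group. The benefit also requires a baseline direct-cost figure that the plan does not yet define.

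**What to change.** In Section 4.6, replace the raw cost difference with wording such as:

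> Incremental cost will be the arm coefficient from a linear regression of total follow-up cost on arm and baseline cost, refitted within each bootstrap resample used for the ICER and CEAC, with the unadjusted difference as a sensitivity analysis. Baseline cost will cover the 3 months before baseline, use the same unit prices as follow-up, and match the perspective analysed: direct medical costs from hospital and pharmacy records for the payer analysis, plus patient-reported indirect costs for the societal analysis.

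In Section 4.4.1.2, state the same 3-month window for direct costs.

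The cost is one regression inside a bootstrap that is already planned, and a look-up of the prior 3 months in existing hospital and pharmacy records. No extra patients or visits are needed. If recall is noisy or r is low, the gain will be modest, but the adjusted difference remains essentially unbiased under randomisation.

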4.7 Risk and Benefit to study participants

The study contributes minimal or no risk to the participants. This study may improve the medication adherence for participants.

4.8 Risk Benefit Assessment

As stated above, this study contributes minimal or no risk to the participants. As this study involves questionnaire survey, participants are requested to spend 15 to 30 minutes to complete questionnaires carefully and truthfully.

4.9 Ethical Consideration

For government hospitals, ethical approval will be sought from the Medical Research Ethics Committee (MREC), meanwhile PPUM-MREC will be sought for PPUM research site.

5.0 Conflict of Interest

There is no conflict of interest to declare.

5.1 Privacy and Confidentiality

Data will be kept at Universiti of Malaya (UM). Primarily only investigators in the study will have access to the research data. However, individuals involved in this sub-study, qualified monitors and auditors, the sponsor or its affiliates and governmental or regulatory authorities may inspect and copy research, where appropriate and necessary. Any unused sample that has not been processed in research will be destroyed. Information that was extracted from medical records will not be destroyed until 7 years after the last publication. Results that will be obtained from this study will be published, presented, and shared with other researcher, scientist and community. In Caringup system, the user (patient/family) data is owned by the user. The user can delete their data at any time. The data from all the repositories can be erased as bounded by the General Data Protection Regulation (GDPR). The personal data will be encrypted and stored in Microsoft Azure cloud. A user (patient or family members) will get Data Privacy Policy in English and Malay when signing up to use CareAide app. No data will be transmitted from hospitals such as UMMC, Hospital Putrajaya and Hospital Pulau Pinang to CaringUp company. The data of the patients who participate in the study will be provided by CaringUp to research team. Patient data is owned by patient. They can delete at any time according to the regulation.

5.2 Publication Policy

No personnel information will be revealed, and subjects will not be identified when the findings of the results are published. Permission from the Director General of Health, Malaysia will be obtained prior to publication.

